4.0 Study Endpoints

*4.1 Describe the primary and secondary **study** endpoints. See links below for discussion of study endpoints and how they may differ from study objectives. These are most common in clinical trials but are sometimes applicable to other types of biomedical research, as well as social, behavioral, or educational research. See link below for a discussion.*

https://docs.google.com/document/d/1Wocz7K7a0hCQJPPO_khh5l1SQjhGDDGHzcOPRHR5Tw/edit?usp=sharing

Primary study endpoints are indirect calorimetry measurements, blood glucose measurements, beverage condition ratings and preferences (behavioral measures), and brain activation measured by fMRI.

*4.2 Describe any primary or secondary **safety** endpoints. These should be included for all studies that are greater than minimal risk. (Minimal risk: The probability and magnitude of harm or discomfort anticipated in the research that are not greater in and of themselves than those ordinarily*

encountered in daily life or during the performance of routine physical or psychological examinations or tests.):

There are no safety endpoints.

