5.0 Study Design and Statistical Analysis Plan

5.1 *Describe the basic study design/approach (e.g., qualitative study using five focus groups of first year students to describe assimilation into the university community; randomized controlled trial of a behavioral change intervention to increase dietary intake of whole grains; pre- post-test evaluation of new pedagogical techniques to improve adult literacy):*

The pilot study will be a within-subjects design used to compare ratings of beverages with different levels of sweetness provided by different sugars and non-nutritive sweeteners (see 7.0:Investigational Agents: Beverage Solutions, below, for ingredients).

The overall study will be a within-subjects (crossover) design used to compare behavioral (beverage ratings and preferences), metabolic (blood glucose & metabolites, indirect calorimetry measures), and brain activation responses (fMRI) to glucose-, fructose-, and sucrose-containing beverages (Aim 1); and sucrose-, high fructose corn syrup (HFCS)-, and non-nutritive sweetener + sucrose- containing beverages (Aim 2).

5.2 *Describe corresponding data analysis plan/approach (e.g., content analysis of focus group transcripts; descriptive analysis followed by linear regression modeling; nonparametric analysis of pre- and post-test measures):*

Linear mixed effects models will be used to assess the following outcome variables: change in indirect calorimetry measures, change in blood glucose and insulin, change in beverage liking. Linear regression will be used to relate blood and indirect calorimetry measures to liking and other subjective ratings.

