Participants will be trained on how to use standard perceptual rating scales used in the study. Then, they will taste, rate, and rank each mixture using these scales. All mixtures will be within common sweetness concentrations found in commercially available beverages (i.e., we will not provide sugar or non-nutritive sweetener amounts that would commonly cause gastrointestinal discomfort in most people). Data from this pilot study will then be used to determine acceptable concentrations of sugars and non-nutritive sweeteners to be used in the full study.

FULL STUDY:

OVERVIEW:

Approximately 200 participants will be recruited from the general public for this randomized crossover study conducted at the FBRI. Our goal is to have approximately 140 participants complete the study. The duration of participation will be no more than 6 weeks for each aim. The figure above depicts the overall study design and procedures for both Aims 1 and 2. The study design is the exact same for Aims 1 and 2, but the beverages selected for conditions "CS1, CS2, and CS3" are different, depending on aim. For Aim 1, conditions will include fructose, glucose, and sucrose. For Aim 2, conditions will include sucrose, high fructose corn syrup (HFCS), and non-nutritive sweetener+sucrose. Each CS drink will be consumed over a 1-week period in sequential weeks without "washout" weeks in between.

Recruitment and Screening:

Approved study recruitment materials will be distributed in the following ways. Flyers will be posted on bulletin boards and approved posting sites throughout Roanoke, Blacksburg, and surrounding areas. Digital advertisements will be displayed on [name] lab and CHBR social media, VT News, and in list serves with permission. All advertisements will include a link to the lab website where there will be approved language describing the research study. Interested participants will fill out a general screening survey. All screening surveys will be delivered through Ripple (a HIPAA-compliant, secure database software; see section 9.4 for description). This screening survey will be used to determine study eligibility. Once the general screening survey has been completed, participants who may be eligible for this study will be contacted via email (see attachment 'Screening email'). If participants choose to complete the study-specific screening form and are eligible for this study, they will be contacted to schedule a consent session.

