Participants will rate their hunger, thirst, and fullness on standard visual analog scales while fasted and after consumption of the beverage, along with perceptual ratings about the beverages consumed during the session.

IV Blood Draws

An IV catheter will be inserted into the participant's arm for venous blood draws throughout the session. This catheter will remain in the participant's arm for the duration of the session (~4 hours). A fasting baseline draw will be made, and then six additional blood draws after the participant consumes the conditioning beverage will be conducted throughout the remaining session. Two tubes of no more than 5 ml each will be collected at each blood draw (14 tubes total). This is approximately 126 ml of blood in total (~8-9 tablespoons). This is roughly equivalent to 1/4 the amount of blood given during a typical blood donation. All blood draws will occur while the participant is reclining on a bed inside a metabolic chamber (see Metabolic Chamber Indirect Calorimetry below). For the draws, the researcher performing the blood draws will reach their arms into the chamber via ports on the side of the chamber walls. Participants will be able to communicate with research personnel using a 2-way intercom system, and the walls of the metabolic chamber are clear plexiglass that allow researchers and participants to see each other throughout the measurement. IV blood draws occur concurrently with metabolic chamber measurements (see below). The IV catheter line will be flushed with normal saline between each blood draw to prevent coagulation in the catheter tubing. After the final blood draw, the catheter will be removed and the venipuncture site secured with sterile tape or bandage. Should the IV catheter placement fail or become unusable during the session, the catheter will be removed and participants will continue with the metabolic chamber indirect calorimetry portion of the session.

Metabolic Chamber Indirect Calorimetry

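### Section 5.2 analyses change from a single fasting draw and specifies neither baseline adjustment nor a session-level term, so the glucose and insulin beverage tests could be imprecise or, under a participant-only model, too liberal

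*Combined protocol and SAP*

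**What the plan says.** - **Sampling.** Section 8.2 (IV Blood Draws) states: "A fasting baseline draw will be made", followed by "six additional blood draws after the participant consumes the conditioning beverage". That is seven draws per session. The tube count agrees: two tubes per draw and 14 in total.
- **Sessions.** Each participant has three in-person sessions, one per beverage. Section 8.2 (Overview) says: "For Aim 1, conditions will include fructose, glucose, and sucrose". Aim 2 has the same layout with three other drinks.
- **Model.** Section 5.2 lists the mixed-model outcomes as "change in indirect calorimetry measures, change in blood glucose and insulin, change in beverage liking". It names no fixed effects, random effects, residual covariance or baseline covariate. It does not say whether the six post-drink values enter singly or as one summary per session.
- **Status.** Section 4.1 reads: "Primary study endpoints are indirect calorimetry measurements, blood glucose measurements", followed by ratings and fMRI. Insulin is not on that list.
- **Size.** Section 14.1 plans 70 completers per aim and refers to power calculations whose inputs are not shown.

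**The concern.** Two features of the design interact.

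First, all six changes in a session subtract the same fasting value. If that value happens to be high, all six changes are low together. This correlates changes within a session over and above anything a participant effect captures.

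Second, beverage varies only between sessions. The correct yardstick for its main effect is therefore session-to-session variation, not draw-to-draw variation. A mixed model with a participant intercept and nothing at session level treats 18 values per participant as independent given the participant, and so tests beverage against an error term that is too small.

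At stake is the comparison of sugars on blood glucose, a primary endpoint, and on insulin. Even with the error term right, a raw change score carries the full noise of one draw into each comparison when the same baseline could be used more efficiently.

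**Working it through.** **Figures that can be checked first.** The plan states no error rate for this analysis. The 70 per aim cannot be recomputed, because no alpha, power, effect size or SD is given. The recruitment arithmetic agrees: 140 / (1 − 0.30) = 200. So does the tube count: (1 + 6) × 2 = 14.

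**Inputs.** From the documents: n = 70 participants, b = 3 beverages, t = 6 changes per session. Assumed: alpha 0.05, and k = SD of baseline noise / SD of post-drink draw noise, between 0.25 and 1.0.

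**Step 1: correlation from the shared baseline alone.** ρ = k² / (1 + k²).
- k = 0.25: 0.0625 / 1.0625 = 0.06
- k = 0.5: 0.25 / 1.25 = 0.20
- k = 1.0: 1 / 2 = 0.50

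**Step 2: correct error for beverage versus the error a participant-only model uses** (in units of the within-participant variance of one change).
- Correct, session level: λ = 1 + 5ρ, on (70 − 1)(3 − 1) = 138 df.
- Draw level: 1 − ρ, on 70 × 3 × 5 − 3 × 5 = 1,035 df.
- A participant-only model pools them: M = [138λ + 1,035(1 − ρ)] / 1,173.
- The variance of a beverage contrast is understated by the factor V = λ / M.

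At ρ = 0.06: λ = 1.30, M = (179.4 + 972.9) / 1,173 = 0.982, V = 1.32.

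At ρ = 0.50: λ = 3.50, M = (483 + 517.5) / 1,173 = 0.853, V = 4.10.

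**Step 3: false-positive rates.** Omnibus (2 df): exp(−5.991 / 2V). Pairwise: 2Φ(−1.96 / √V).

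| ρ | V | Omnibus | One pairwise contrast |
|---|---|---|---|
| 0.06 | 1.32 | 10% | 9% |
| 0.20 | 2.12 | 24% | 18% |
| 0.33 | 2.96 | 36% | 25% |
| 0.50 | 4.10 | 48% | 33% |

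Simulation (4,000 null trials per scenario) gives 10% / 9%, 25% / 18%, 36% / 25% and 46–49% / 32–33%. A REML fit of the participant-only model at ρ = 0.50 (150 trials) gives 48% / 33%. With a participant-by-session intercept added, the rates are 4.2% to 6.0% (omnibus) and 4.5% to 5.8% (pairwise) in every scenario.

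**Step 4: what else moves the rate.** With independent draws and no baseline noise the rate is the nominal 5%. AR(1) correlation of 0.5 between draws, with no baseline noise at all, gives 30% / 22%, so the shared baseline is not the only route. The beverage-by-time test goes the other way: its true error, 1 − ρ, is smaller than M, and it rejects about 0% to 4% of the time in the shared-baseline scenarios.

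**Step 5: covariate versus subtraction.** Take one post-drink mean per session. Let a session-level shift with SD s (in units of draw noise) be common to baseline and later draws, with equal noise on all draws.
- Raw change: variance 1 + 1/6 = 1.167.
- Adjusted for baseline at its within-participant slope: 1/6 + s² / (s² + 1).

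| s | Adjusted | Reduction against 1.167 |
|---|---|---|
| 0 | 0.167 | 86% |
| 1 | 0.667 | 43% |
| 2 | 0.967 | 17% |

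Because s² / (s² + 1) is below 1, adjustment is never worse under this model.

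**The case against.** The strongest reply is that the model criticised is not in the documents. Section 5.2 says mixed models and stops. Nothing shows that the team intends a participant-only intercept, nor that six separate changes are the outcome; a peak or an area under the curve would also fit the wording, and then the wrong-error-term problem does not arise. This stands. The sampling scheme in 8.2 has no fault in itself; the gap is in 5.2.

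Three stronger readings are tempting and are not supported:
- *The planned glucose results will be falsely positive.* The plan does not commit to the faulty model, so inflation is a risk left open, not a stated error.
- *Calorimetry is affected in the same way.* Section 8.2 describes a fasting measurement of about 30 to 60 minutes and a post-drink measurement of about 3 hours. It does not say that serial values are analysed, and a baseline of that length is not one draw, so the figures above do not carry over.
- *The error rate is near 50%.* That needs baseline and post-drink noise to be equal and concerns the omnibus test. The hypotheses in 2.2 compare particular drinks, for which the pairwise column is closer.

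It can also be said that once a session term is present, change scores hold about 5%, so baseline adjustment is not needed for error control. That is correct. The case for the covariate rests on precision (step 5).

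**Conclusion.** The point holds as a conditional one. Section 5.2 permits an analysis of glucose and insulin in which the beverage main effect is tested at about 10% to 48% (omnibus) or 9% to 33% (one pairwise contrast) instead of 5%. These figures rest on alpha 0.05, 70 complete participants, draws entered singly, a participant-only random intercept, and a within-session correlation of 0.06 to 0.50 due to the baseline alone. None of these except the 70 is in the documents, and serial correlation between draws would raise the rates. It would be wrong to infer that every test is too liberal, since beverage-by-time becomes conservative.

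Separately from the error rate, the change outcome that 5.2 does state gives up precision that the fasting draw already collected could supply: a 17% to 86% lower variance for a beverage contrast over assumed session-shift SDs of 0 to 2 times draw noise. This is worth settling before analysis, because blood glucose is a primary endpoint.

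**What to change.** In 5.2, for glucose and insulin, and for calorimetry only if it is analysed as serial values:

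1. State whether the post-drink values enter singly or as one summary per session.
2. Include the session's own baseline value as a covariate and do not rely on a raw change score.
3. If values enter singly, fit fixed effects for beverage, time, beverage-by-time and period, with random intercepts for participant and for participant-by-session, or an equivalent within-session covariance.
4. A valid alternative is one post-drink summary per session, adjusted for that session's baseline. It is not equivalent: it gives a sound beverage test but no beverage-by-time test.

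The cost is a few lines of SAP text and one extra random term. Intervals become wider where they would have been falsely narrow. No additional draws, visits or participants are needed.

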9.0 Data and Specimen Long Term Storage and Use

9.1 If you will store data or specimens for future use, describe where you will store the data or specimens, how long they will be stored, and how and by whom the data or specimens will be accessed:

Indirect calorimetry data will be stored on a secure network drive provided by FBRI. Behavioral (e.g., last time food eaten before measurement, last bout of exercise before measurement, etc.), anthropometric, responses to questionnaires, and pertinent metabolic variables will be stored in FBRI's

instance of REDCap. Data will be stored indefinitely for future analysis and use in developing future protocols. Only individuals with FBRI access to secure network drives and FBRI's instance of REDCap will have access to stored data. Plasma and/or serum aliquot samples will be frozen and stored for future analysis of insulin and other metabolites. Additional aliquots of plasma and/or serum will be stored indefinitely after the completion of data analysis to allow for replicate testing to ensure data quality and for additional analyses as the field moves forward.

9.2 For specimens, list the data to be stored or associated with each specimen:

Serum and plasma blood samples for storage will be labeled with the participant's 4-digit ID number, date collected, and conditioning beverage associated with that sample.

9.3 Describe the procedures to release data or specimens outside of the research team, including the process to request a release, approvals required for release, who can obtain data or specimens, and what data will be provided with specimens:

No specimens will be released.

9.4 Describe the identifiers to be included with stored data or specimens, as well as any key or code that could be used to make them identifiable. Describe where the code will be stored, who will have access to it, and when it will be destroyed:

Data will be coded using a 4-digit sequentially-generated ID number unique to each participant. The key linking the participant name or identifiable information and the ID number will be stored in Ripple.

Ripple is a secure web application designed for storing and managing personal identifiable information of research participants. Ripple was initially developed at the University of Michigan to provide a user-friendly, web-based secure interface where research teams can centralize the storage and management of research participants' personal information. Information stored in Ripple is kept in fully encrypted format inside dedicated databases that are segregated from other Ripple accounts and thus only authorized study staff will have access to the study data. Likewise, Ripple infrastructure complies with the privacy and security guidelines of the Health Insurance Portability and Accountability Act

(HIPAA), including 2048-bit data encryption in transit and at rest, automatic logoff, audit trail, daily backups in triplicate dedicated servers, firewall, custom access permission for lab members, zxvcvn password strength estimation, and enterprise administrative safeguards to prevent unauthorized staff from accessing participant information. Only personnel who are direct members of the research team will have access to personally identifiable information stored in Ripple. The link between the coded designation and personal information will only exist on this secure platform.

All study data will be encrypted and kept on either a server or FBRI's instance of REDCap, both managed by FBRI's Information Technology (IT). Only authorized research team members, who have authorized FBRI IT-assigned credentials, will be able to access the network drive server and REDCap.

Any paper documents, such as signed consent forms and MRI safety forms, will be stored in a locking filing cabinet accessible only by authorized research team members.

Per Virginia Tech policy in order to compensate participants, social security number (or Taxpayer ID) and mailing address will be collected via a W-9 or W-8BEN form. The participant address and SSN will be entered into the ClinCard system, which is a HIPAA-compliant payment system approved by Virginia Tech. After entry, this form will be given to and stored by the central administration at the FBRI to be used if it is required that a tax statement be sent to the participant, based on Federal Income Tax regulations. Study staff will not store documents with SSN or address used for the purpose of payment.

Identifiable information will be destroyed at the written request of the participant.

9.5 Please select the identifiers you will obtain (whether directly from participants or from another source), including but not limited to:

	Name
	Geographical subdivisions smaller than a state, including street address, city, county, precinct, zip code, and equivalent geocodes (note, the initial three digits of a zip code are not considered identifiable)
	Elements of dates (except year) for dates directly related to an individual, including birth date, admission date, discharge date, date of death, and single year of age over 89 and all elements of dates (including year) indicative of such age (note, such ages and elements may be aggregated into a single category of age 90+)

	Phone numbers
	Fax numbers
	Electronic mail addresses (e-mail)
	Social Security numbers
	Medical record numbers
	Health plan beneficiary numbers
	Account numbers
	Certificate/license numbers
	Vehicle identifiers and serial numbers, including license plate numbers
	Device identifiers and serial numbers
	Web Universal Resource Locators (URLs)
	Internet protocol (IP) address numbers
	Biometric identifiers, including finger and voice prints (audio recording)
	Full face photographic images and any comparable images (including video recording)
	Student record number or identification number
	User name for online or computer accounts
	Any other unique identifying number, characteristic, or code (note this does not mean the unique code assigned by the investigator to code the data): Click here to explain.

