Ripple (see section 9.4 for Ripple description) will be used to collect screening information. Information about the beverages participants will be consuming at home as well as dietary, physical activity, and behavior information will be collected through REDCap. MRI safety information will be collected via paper form (included in supporting documents). Perceptual ratings will be collected using a laptop or tablet and custom scripts written in R or Python (PsychoPy). Blood glucose will be measured using a Hemocue point-of-care system, and insulin will be measured using the Immunolite 1000 Immunoassay System or ELISA. Other blood metabolites will be measured from stored samples using ELISAs or other appropriate wet lab equipment and techniques. Brain images will be acquired during fMRI scans. Metabolic measurements will be collected using a metabolic chamber from MEI Research, Ltd. All data collected during the study will be stored on FBRI's instance of REDcap and/or FBRI's secured server.

8.5 Who will transcribe or code audio and/or video recordings?:

There will be no audio or video recordings.

8.6 Include a description of any deception to be used in the study. Include justification for the use of deception (why the deception is necessary), describe the debriefing process, and describe how the study meets all the following criteria for alteration of consent (deception is considered an alteration of informed consent):

- *The research involves no more than minimal risk to the subjects*
- *The alteration will not adversely affect the rights and welfare of the subjects*
- *The research could not practicably be carried out without the alteration/deception*
- *(Optional but encouraged in most cases) Subjects will be provided with additional pertinent information after participation (i.e., debriefing for studies involving deception)*

There will be no deception.

8.7 If the study involves long-term follow-up (once all research related procedures are complete), describe what data will be collected during the follow up period and when it will occur:

There are no long-term follow-ups.

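### Section 9.2 puts the conditioning beverage on stored blood tubes, so staff assaying insulin and other stored-sample metabolites can see the condition when linkage does not require it

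*Combined protocol and SAP*

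**What the plan says.** Section 9.2 states that the label on serum and plasma samples for storage will give the participant's ID, "date collected, and conditioning beverage associated with that sample". Section 9.1 gives the purpose of these samples: "Plasma and/or serum aliquot samples will be frozen and stored for future analysis of insulin and other metabolites". It adds that further aliquots are kept indefinitely once data analysis is complete, partly "to allow for replicate testing to ensure data quality". Section 9.3 says that specimens will not leave the research team.

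Section 8.4 gives the methods. For insulin, "insulin will be measured using the Immunolite 1000 Immunoassay System or ELISA". For the rest, "Other blood metabolites will be measured from stored samples using ELISAs or other appropriate wet lab equipment and techniques". Glucose is handled differently: "Blood glucose will be measured using a Hemocue point-of-care system".

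Section 5.2 names change in insulin, with change in glucose, as an outcome for the mixed models. Section 1.0 includes blood metabolites in the primary objective. Section 4.1 lists glucose, but not insulin, among the primary endpoints. Section 8.2 describes a "randomized crossover study conducted at the FBRI". No section describes masking of participants, session staff, assay staff or analysts. Section 19.1, on quality control, relies on staff training and gives no rule for repeating an assay or excluding a value.

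**The concern.** An immunoassay reading leaves little room for the operator's expectation. The decisions around it leave more: whether an odd value is run again, which of two results is kept, and whether a value is dropped. If the person deciding can read the condition off the tube, those decisions can differ by condition without anyone intending it. The hypotheses in Section 2.2 are directional (sucrose above fructose or glucose in Aim 1, high fructose corn syrup above the other two drinks in Aim 2), so staff may have an expectation about the drinks.

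At stake are the between-beverage contrasts in insulin and the other metabolites measured from frozen samples, and the study's ability to report that those assays were run without knowledge of condition. Samples are kept indefinitely, so the label would also reveal the condition in any later assay.

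**Working it through.** The plan gives no figure to reproduce on this point. The check sets the sections side by side, with a few counts for scale.

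**1. Which measurements come from the labelled tubes?** Section 9.2 covers samples for storage. Section 9.1 assigns the frozen aliquots to insulin and other metabolites, and Section 8.4 agrees for the other metabolites. Glucose is read on a point-of-care device. Calorimetry comes from the metabolic chamber, ratings from a laptop, tablet or survey, intake and choice from the post-test session, and brain activation from the scanner. Only insulin and the other stored-sample metabolites pass through a tube carrying this label.

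**2. Does anything else hide the condition from the assayer?** No outside laboratory stands between the team and the assay, because specimens are not released. No section provides for coded labels, a withheld key or masked assay staff.

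**3. Is the beverage needed on the tube?** Section 8.2 gives each drink its own week and places in-person sessions at least 3 days apart. No two sessions of one participant share a date, so each pair of ID and date belongs to one session and one beverage. The study database can make the link, and removing the beverage from the label loses nothing that the analysis needs.

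**4. Is the listed label otherwise sufficient?** Section 8.2 plans one fasting draw and six later draws, 1 + 6 = 7 per session. The listed items include no draw number or time, so ID, date and beverage do not tell the seven draws of a session apart. A session-and-draw code would also close that gap.

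**5. How many tubes?**
- Tubes per session: 7 draws × 2 tubes = 14, as Section 8.2 states.
- Planned aim completions (Section 14.1): 70 + 70 = 140. A participant who completes both aims counts twice.
- Draw points: 7 × 3 sessions × 140 = 2,940.
- Collected tubes: 2,940 × 2 = 5,880.

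These are planned counts. Failed catheters would lower them and partial completers would raise them. The number of aliquots per tube is not given.

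**6. Would the protocol's own condition names serve as a code?** Section 8.2 ties CS1, CS2 and CS3 to beverages by aim and mentions no participant-specific mapping. If the mapping is the same for everyone, anyone who knows it can read the sugar from the code, so it would mask little.

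**The case against.** The strongest case against has four parts.

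- **The protocol never promises masked assays.** Section 9.2 answers a form prompt about data kept with specimens and is not an assay procedure. This is right: nothing is contradicted. The point concerns a missing safeguard.
- **The text does not say what form the beverage entry takes.** It could be a sugar name, a flavour or a condition code. This stands as a caveat. The plain reading is the beverage itself. If a participant-specific code is meant, one clarifying sentence largely settles the matter.
- **The replicate-testing sentence does not show discretionary repeats entering the main analysis.** It concerns additional aliquots kept after data analysis is complete. This also stands. A reader might infer from it that selective repeats will shape the main insulin results, but the documents describe no such repeats, no choice among replicates and no outlier removal. What remains is that these decisions, if they arise, have no stated rule and would be made with the condition in view.
- **The assays are instrument-read, and insulin is not a listed primary endpoint.** Both are true, and they limit the size of the problem. They do not remove it, because insulin is a named model outcome and blood metabolites are in the primary objective.

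A reader might also infer that the label threatens the primary glucose endpoint, or the liking ratings, intake and take-home choice. The documents do not support either inference. Glucose is not described as a stored-sample assay, and a label on a frozen tube cannot reach what a participant rates, drinks or chooses. The documents do not say what is printed on the bottles, so nothing about participant masking follows from Section 9.2.

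**Conclusion.** The point holds as a minor, easily corrected weakness. As written, Section 9.2 lets in-house staff see the condition when they assay, repeat or exclude insulin and other stored-sample metabolite values, and the beverage serves no linkage purpose on the tube. The likely bias is small and cannot be quantified from the documents. No sample size, power or error-rate figure changes.

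The conclusion rests on three assumptions: that the beverage entry identifies the condition; that assay staff do not already know each participant's beverage order by another route; and that any metabolite techniques not yet named are read by instrument, as the named ones are. If the second assumption fails because the same people run sessions and assays, a code built from ID and session number gives little protection and a random code is preferable.

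**What to change.** In Section 9.2, replace the beverage entry with a neutral sample code. Two forms would work:

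- participant ID plus session number and draw number, with sessions numbered across both aims for anyone who takes part in both; or
- a random code for each sample, linked to ID, session and draw in the study database.

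A fixed CS1/CS2/CS3 mapping should not be used.

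Add two sentences. One should say that the allocation key is kept from assay staff until assay values and exclusions are locked. The date and session number can be decoded by anyone holding the allocation, so the code protects only if the key is withheld. The other should say that any rule for repeating an assay, choosing between results or excluding a value is written down and applied before unmasking.

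The cost is a label change, a code list, and a named role to hold and document the key. If samples have already been stored under the present label, they could be recoded before assay, or the report could state that they were assayed with the condition visible.
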